6.2.3 Per-protocol (PP) Population

Per-protocol (PP) Population: Subjects in the ITT Population who have undergone insertion of the study catheter and AF ablation procedure, and do not have other major protocol violations. The definition of major protocol violations includes but not limited to:

- Serious violation of the inclusion/exclusion criteria, and the subjects are allowed to continue the clinical trial;
- Violation of informed consent (e.g.: no informed consent is conducted, the signature and/or the date of the informed consent form is missing; The time signed is after the procedure; Both the two copies of ICF are kept in the study site)
- No transesophageal echocardiography (TEE) examination is conducted within 24 hours before the procedure; (Applicable to the document “A Description of SMART CHINA Study Protocol Violations/Deviation Report to Institutional Ethics Committee(IEC)” developed on June 20, 2015)
- No examination to detect LA thrombi is conducted before the procedure; (Applicable to the document “A Description of SMART CHINA Study Protocol Violations/Deviation Report to Institutional Ethics Committee(IEC)” developed on January 18, 2016)
- THERMOCOOL® SMARTTOUCH™ catheter is not used or is used repeatedly during the procedure
- CARTO®3 V3.2 or the later version and VisiTag™ software is used for data collection during the procedure
- No isoproterenol is used to confirm entrance block 30 minutes after the procedure
- Agilis sheathing canal in combination with THERMOCOOL® SMARTTOUCH™ catheter is used during the procedure

Repeated ablation treatment is conducted during the blanking period, PP population will be used to provide supportive analysis for efficacy endpoints.

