Study participants who undergo PVI are to have their procedure performed and completed (as described in section 5.4) using the study device in conjunction with the CARTO® 3 System (version 3.2 or higher), an electro-anatomic mapping system for use in performing catheter-based electrophysiological RF ablation procedures. All devices to be used in this study are commercially available, conform to the applicable local regulations and are to be used according to the approved indication and their Instructions for Use (IFU). Each site will be required to have specific equipment for performing RF ablation procedures. Sites will be instructed to refer to the User's Manual / Instructions for Use for the set-up of system / device / component.

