3.3 Number of Centers

Up to 15 sites in China will participate in this study. Total enrollment among all sites of up to 200 subjects is expected. Sites participating in this study will be selected based upon their capabilities to successfully carry out those assessments.

CPVI will be performed by experienced operators who have prior experience with the NAVISTAR® THERMOCOOL® and/or EZ STEER® THERMOCOOL® NAV catheters (>50 AF ablation case per year). Before study initiation, operators will be trained on the use of the CF-guided ablation catheter and CARTO®3 VisiTag module for at least 5 patients. Investigators will set

personal operating reference ranges using experience gained from this training and the information of the prior clinical (human) studies and published literature. These patients will not be included in the study.

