4.1 Primary Efficacy Endpoint

The primary effectiveness endpoint for this study is freedom from documented symptomatic

atrial fibrillation (AF), atrial tachycardia (AT), or atrial flutter (AFL) episodes through 12-month follow-up after the index ablation procedure (includes a three-month blanking period).

AF/AFL/AT qualifies as an arrhythmia recurrence after the first ablation if it lasts ≥ 30 seconds and is documented by ECG, HM or TTM, etc.

The following indicators will also be considered primary effectiveness failures and will be included in the effectiveness analysis population:

- Acute procedural failure (i.e., failure to confirm entrance block in all pulmonary veins with an isoproterenol intravenous challenge 0.5h post procedure or use of a non-study catheter to treat PAF)
- A repeat ablation beyond the 90-day blanking period

Atrial tachycardia/fibrillation atrial/auricular flutter recurrence events will be recorded and included in study analysis after a 90-day blanking period; recurrence during the blanking will not be considered treatment failure; re-ablation will not be recommended during the blanking^{1,2}.

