6.3.2 Protocol Deviation

Major protocol deviation will be summarized, and the follow-up period and reason for major protocol deviation will be classified and summarized. List of major protocol deviation will also be presented.

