6.4 Ablation Parameters

Descriptive analysis is conducted for ablation procedure parameters, and the procedure parameters include:

- Total X-ray fluoroscopy dose (mGr)
- Intraoperative transcatheter fluid infusion (ml)
- The maximum infusion rate of the intraoperative transcatheter fluid (ml/min)
- Whether the subject has been observed for 30 minutes after CPVI
- Whether isoproterenol has been given to induce fibrillation atrial 30 minutes after CPVI
- Whether other drugs have been given to induce fibrillation atrial 30 minutes after CPVI
- Whether an immediate success has been achieved
- Whether the exit block has been observed
- Presence of linear ablation
- Presence of other ablation
- Whether the sheathing canal has been used during the procedure
- Whether CART03 version 3.2 or later version has been used to mapping the left atrium before radiofrequency ablation
- Whether the VisiTag module has been used
- Whether radiofrequency discharge is conducted
- Average power (watt)
- Average temperature (C)
- CF
- Number of PV reconnection targets
- Procedual time, ablation time and fluoroscopy time
- The longest duration of one-time single discharge (second)
- The maximum decrease in impedance value (ohm)
- Presence of any other types of spontaneous arrhythmia during the procedure

- Presence of any other types of induced arrhythmia during the procedure

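### SAP 6.2.3 lists use of the required CARTO 3 version, together with VisiTag, as a major violation that removes a subject from the per-protocol population

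*SAP*

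**What the plan says.** SAP 6.2.3 takes PP to be the ITT subjects who had the study catheter inserted, had the ablation, and had no other major protocol violation. It then gives an open-ended list of such violations. One bullet is "CARTO®3 V3.2 or the later version and VisiTag™ software is used for data collection during the procedure".

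Protocol 1.3 says the procedure is to be performed and completed "using the study device in conjunction with the CARTO® 3 System (version 3.2 or higher". SAP 1.3 repeats this.

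VisiTag is treated differently. Under Protocol 3.3 and SAP 3.3, "operators will be trained on the use of the CF-guided ablation catheter and CARTO®3 VisiTag module for at least 5 patients", and its use is recorded, but no sentence makes it compulsory. SAP 6.4 lists two relevant procedure fields: "Whether CART03 version 3.2 or later version has been used to mapping the left atrium before radiofrequency ablation" and "Whether the VisiTag module has been used".

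The list in SAP 6.2.3 is followed by "Repeated ablation treatment is conducted during the blanking period, PP population will be used to provide supportive analysis for efficacy endpoints". On the primary endpoint, SAP 4.1 counts as a failure "A repeat ablation beyond the 90-day blanking period", and Protocol 4.1 does the same.

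SAP 6.5.1 makes ITT the main analysis of the primary endpoint and PP the supportive one. SAP 6.3.2 adds: "Major protocol deviation will be summarized, and the follow-up period and reason for major protocol deviation will be classified and summarized".

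**The concern.** The bullet stands in a list of reasons to remove a subject from PP, yet it describes what the protocol asks sites to do. A programmer who follows the text removes the subjects who complied on this item. One who notices the problem has to guess the intended rule, and the guess is not simple, because the bullet joins two tools and only one of them is required.

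At stake are the make-up of the supportive analysis and, if the same wording is used there, the summary and listing of major deviations under SAP 6.3.2.

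The sentence on repeat ablation leaves a second gap. The text does not settle whether a subject re-ablated during blanking belongs in PP. Early re-ablation is not itself a primary failure, so such a subject can be a success in ITT.

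**Working it through.** The bullet contains no figure, so the check compares texts and then works through the logic.

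**Step 1: is the positive wording just the style of the list?** The other procedural bullets in SAP 6.2.3 compare with the protocol as follows.

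| Item | Status in the documents | Wording of the SAP 6.2.3 bullet |
|---|---|---|
| TEE or other check for left atrial thrombus | part of the pre-procedure assessments (Protocol 5.3) | negated (two bullets) |
| Study catheter | the only study catheter (Protocol 1.3) | negated, plus repeated use |
| Isoproterenol challenge | listed in the procedure (Protocol 5.4) | negated |
| Agilis sheath | barred (Protocol 5.4) | positive |
| CARTO 3 V3.2 or later, with VisiTag | CARTO version required (Protocol 1.3, SAP 1.3) | **positive** |

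Expected items are worded as absent, and the barred item is worded as present. The CARTO/VisiTag bullet is the only expected item worded as present. That points to a lost negation.

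**Step 2: does anything else correct it?** No. The PP definition in Protocol 8.3 does not itemise violations. SAP 8 (changes to planned methods) and SAP 9 (data processing) both say there is nothing to report. SAP 10 and SAP 11 place the programming specifications and mock tables in separate documents, which were not available for this check.

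**Step 3: what does each reading do?** Let C mean that CARTO 3 V3.2 or later was used and V that VisiTag was used. The literal bullet removes (C and V). Putting the negation back allows three rules: (a) remove not-C; (b) remove not-C or not-V; (c) remove only if neither was used.

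| Subject | Literal | (a) | (b) | (c) |
|---|---|---|---|---|
| C, V | removed | kept | kept | kept |
| C, not V | kept | kept | removed | kept |
| not C, V | kept | removed | removed | kept |
| not C, not V | kept | removed | removed | removed |

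The first and last rows are reversed under every restored reading. The middle rows depend on a choice that the documents do not make. Rule (c) would keep a subject without the required CARTO version, so it does not match Protocol 1.3. Rules (a) and (b) both match it and differ only on VisiTag.

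If both tools were used in all N subjects, the literal bullet leaves N − N = 0 in PP. The documents do not say how often both tools were used, so no other size can be given.

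**Step 4: do the planned fields fit the bullet?** The CARTO field in SAP 6.4 concerns mapping of the left atrium before ablation, while the bullet concerns data collection during the procedure. The documents do not show that these are the same variable.

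**Step 5: is the primary analysis touched?** No. The success rule is an exact two-sided 95% lower bound above 50% in ITT. The design figure reproduces without reference to PP: at n = 150, at least 88 successes are needed, with exact power 0.955 at a true rate of 65% (stated 95%); 150/(1 − 0.20) = 187.5, rounded up to 188.

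**Step 6: repeat ablation in blanking.** Protocol 4.1 and SAP 4.1 make a repeat ablation a failure only after day 90, and say that re-ablation during blanking is not recommended. The phrase in SAP 6.2.3 follows the violation list, but a comma joins it to the sentence on the use of PP. It can be read as a last violation or as a stray clause.

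**The case against.** The strongest reply is that this is a slip whose intended direction is plain. The neighbouring bullets show the pattern, and a literal PP would be so small that the error would be noticed. PP is only supportive. All of this stands, and it limits the point to correcting an operative rule. It does not make the correction unnecessary, because restoring the word does not settle whether VisiTag counts.

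The phrase on repeat ablation may also be a final bullet that lost its marker when the PDF was read. That is possible, and the source layout should be checked, but the comma leaves real doubt.

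Four stronger readings are tempting and are not supported:

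- A reader might infer that PP keeps those who departed from the protocol. The bullet does not remove them, but the list is expressly not exhaustive, so a subject mapped without the required CARTO version could still be excluded as an unlisted major violation.
- A reader might infer that the literal and corrected PP share no subject. That holds, on this item, only if absence of either tool is the violation. If only missing CARTO counts, subjects with CARTO but without VisiTag are in both.
- A reader might infer that VisiTag is mandatory. It is trained on and recorded, but not expressly required.
- A reader might infer that results or deviation listings are in fact wrong. The programming specifications and mock tables are separate documents, so how PP was derived is unknown.

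**Conclusion.** The point holds as an error of wording in an operative definition. SAP 6.2.3 contradicts Protocol 1.3 and SAP 1.3, and neither document corrects it. Followed as written, the bullet removes every subject in whom both tools were used, up to the whole of PP under full use. The size below that limit cannot be stated, because the documents do not give the rate of use.

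The consequence is confined to the PP analysis and, if the wording is shared, to the reporting of major deviations. The superiority claim rests on ITT and is unaffected. That a negation was lost is an inference from the pattern of the list: very probable, but not documented. The status of repeat ablation during blanking is a separate ambiguity in the same section, and the text alone does not resolve it.

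**What to change.** Before PP is assigned:

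1. Restore the negation in SAP 6.2.3 so that not using CARTO 3 V3.2 or later is the violation, in line with Protocol 1.3 and SAP 1.3.
2. State whether absence of VisiTag alone is also a major violation. This is for the sponsor to decide.
3. Name the CRF fields from which the criterion is derived, and confirm that the CARTO mapping field in SAP 6.4 is the intended source or name another.
4. Separate the phrase on repeat ablation during the blanking period from the sentence on the use of PP, and state whether it is a PP exclusion.
5. Check that the programming specifications and the major-deviation summary and listing under SAP 6.3.2 follow the corrected text.

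The cost is a few lines of SAP text and a check of the specifications. No new data should be needed if the fields in SAP 6.4 prove suitable, and the primary analysis and sample size do not change.

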4.0 Study Endpoints

4.1 Primary Effectiveness Endpoint

The primary effectiveness endpoint for this study is freedom from documented symptomatic atrial fibrillation (AF), atrial tachycardia (AT), or atrial flutter (AFL) episodes through 12-month follow-up after the index ablation procedure (includes a three-month blanking period).

AF/AFL/AT qualifies as an arrhythmia recurrence after the first ablation if it lasts ≥ 30 seconds and is documented by ECG, HM or TTM, etc.

The following will also be considered primary effectiveness failures and will be included in the effectiveness analysis cohorts:

- Acute procedural failure (ie, failure to confirm entrance block in all pulmonary veins with an isoproterenol intravenous challenge 0.5h post procedure or use of a non-study catheter to treat the study arrhythmia)
- A repeat ablation beyond the 90-day blanking period

Atrial tachyarrhythmia recurrence events will be recorded and included in study analysis after a 90-day blanking period; recurrence during the blanking will not be considered treatment failure; re-ablation will not be recommended during the blanking^{12,53}.

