8.2 Sample Size and Power Calculation

Assuming the true rate for freedom from documented symptomatic AF, AT, or AFL episodes through 12-months follow-up is about 65% with CF-guided approach and a historic control performance goal of 50%,¹² a sample size of 150 is needed in order to have 95% power to have the lower bound of the two-sided 95% confidence interval of this recurrence free rate above the historic control performance goal. This sample size is computed using nQuery Advisor® version 7.0. Considering 20% dropout rate, a sample size of 188 is needed. This study will enroll approximately 200 subjects (no less than 188).

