4.2.4 Total procedural time, ablation (RF) time and fluoroscopy time

4.3 Safety Endpoint

The incidence of AEs related with the procedure or study catheter

[figure not shown]

Figure 1: Right/left pulmonary veins was divided into 3, 6, 9 and 12 point position from PV to the atrium

5 Sample Size and Statistical Power

Assuming the true rate for freedom from documented symptomatic AF, AT, or AFL episodes through 12-months follow-up is about 65% using THERMOCOOL® SMARTTOUCHTM catheter with Contact Force Sensing Capability and a historic control performance goal of 50%, a sample size of 150 is needed in order to have 95% power to have the lower bound of the two-sided 95% confidence interval of this free-from-recurrence rate above the historic control performance goal¹. The calculation formula⁵⁴ was refer to the paper written by Xinran Tang.

nQuery Advisor® version 7.0 is used for calculation of this sample size. Assuming the dropout rate of the study is 20%, $150 / (1-0.2) = 188$ subjects is needed in total. About 200 subjects are planned to be enrolled in this study (at least 188 subjects).

6 Data Analysis

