6.5 Effectiveness Analysis

6.5.1 Primary Efficacy Endpoint Analysis

ITT population is used for the main analysis of the primary endpoint, and PP population is used for supportive analysis.

The primary endpoint for this study is freedom from documented symptomatic AF, AT, or AFL episodes through 12-months follow-up after the index ablation procedure (includes a 3 months blanking period).

The following will also be considered primary effectiveness failures and will be included in the effectiveness analysis population:

- Acute procedural failure (i.e., failure to confirm entrance block in all pulmonary veins with an isoproterenol intravenous challenge 0.5 h post procedure or use of a non-study catheter to treat the study arrhythmia);
- A repeated ablation after the 90-day blanking period

Atrial tachyarrhythmia recurrence events will be recorded and included in study analysis after a 90-day blanking period. Recurrence during the blanking will not be considered treatment failure.

The number of subjects who achieved this endpoint and its percentage will be presented. A two-sided binomial exact 95% confidence interval will be computed. Superiority against historic control performance goal (50%) after applying THERMOCOOL® SMARTTOUCH™ catheter with contact sensitivity will be claimed if the lower bound of this confidence interval is above 50%.

For the subjects failing to be followed up to the primary endpoint, with conservative consideration, these subjects are considered as primary effectiveness endpoint failure in the main analysis.

Sensitivity analysis will be conducted for the primary endpoints using the methods below:

- For the subjects failed to be followed up to the primary endpoint, the primary endpoint is considered as missing in the analysis, and the subjects will be excluded from ITT analysis set.

A Kaplan-Meier analysis will be performed for the time to the first documented symptomatic AF, AT, or AFL episode. The first quartile, median, third quartile and 95% confidence intervals of the first quartile, median and the third quartile will be computed.

Kaplan-Meier curves for episode time of symptomatic AF, AT or AFL first recorded during 12 months follow-up (Day 91 to 361) after the first ablation will be presented.

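### The per-protocol set drops subjects with no isoproterenol challenge, who are primary failures by definition, and the Kaplan-Meier event is narrower than the primary failure definition

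*SAP*

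**What the plan says.** **Failure definition.** Protocol 4.1, SAP 4.1 and SAP 6.5.1 recognise three routes to primary failure:

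- a documented symptomatic AF, AT or AFL episode after blanking;
- acute procedural failure, meaning entrance block not confirmed in all veins under the isoproterenol challenge, or a non-study catheter used for the study arrhythmia;
- repeat ablation after Day 90.

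For the last two, the protocol says they "will be included in the effectiveness analysis cohorts". SAP 6.5.1 says: "The following will also be considered primary effectiveness failures and will be included in the effectiveness analysis population". Protocol 4.2.1 and SAP 4.2.1 define acute success as block confirmed with the challenge, and repeat that acute failures are primary failures.

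**PP set.** Protocol 8.3 requires study-catheter insertion, an ablation procedure and no other major violation. SAP 6.2.3 gives a non-exhaustive list of major violations, including "No isoproterenol is used to confirm entrance block 30 minutes after the procedure" and that the study "catheter is not used or is used repeatedly during the procedure". SAP 6.5.1 uses PP for the supportive analysis of the primary endpoint.

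**Kaplan-Meier.** SAP 6.5.1 states: "A Kaplan-Meier analysis will be performed for the time to the first documented symptomatic AF, AT, or AFL episode". Protocol 8.4.2 and SAP 6.1 name the same event. Quartiles with confidence intervals and a curve over Days 91 to 361 are planned. No censoring rule is given for acute failure or repeat ablation.

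**Decision rule.** The superiority claim uses ITT: "A two-sided binomial exact 95% confidence interval will be computed", and its lower bound must exceed 50%. Subjects not followed to the endpoint count as failures.

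**The concern.** The endpoint text fixes who is a failure and says that these subjects stay in the effectiveness cohorts. SAP 6.2.3 then removes one kind of failure from the population that is meant to support the primary result. A subject who never had the challenge cannot have block confirmed with it. The same subject is therefore a failure in ITT and absent from PP.

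The Kaplan-Meier curve has a different gap. It will be read beside the primary rate as 12-month freedom after the first ablation, but it counts one of the three routes to failure. A subject with an acute failure, or re-ablated after Day 90, who has no recorded qualifying episode is a failure in the binomial analysis and event-free on the curve.

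At stake is whether the supporting analyses can be trusted to agree or disagree with the primary rate for the right reasons. SAP section 8 reports no change from the protocol's methods, so nothing alerts a reader that PP departs from the inclusion rule.

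**Working it through.** **1. The plan's own figure.** Inputs from Protocol 8.2 and SAP section 5: true rate 65%, goal 50%, two-sided 95% interval, "a sample size of 150 is needed in order to have 95% power", 20% dropout. With an exact binomial interval and n = 150, the smallest success count whose lower bound exceeds 50% is 88 (lower bound 50.3%). Power at 65% is 95.5%. For dropout, 150/(1 − 0.2) = 187.5, so 188. Both stated figures reproduce.

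**2. Which failures SAP 6.2.3 removes.**

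| Primary failure | Listed as a major violation? |
|---|---|
| No isoproterenol challenge, so block not confirmed | Yes |
| Challenge given, block not shown | No |
| Non-study catheter used in addition to the study catheter | No |
| Study catheter not used at all | Yes, but largely covered already by the insertion requirement in Protocol 8.3 |
| Repeat ablation after Day 90 | No; the clause on repeat ablation in SAP 6.2.3 concerns the blanking period |

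The clear conflict is the first row.

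**3. Effect of that one exclusion on PP.** Let f be the share of ITT subjects with no challenge. All are failures, so the numerator is unchanged and the rate becomes 0.65/(1 − f). The documents give no f; the range is assumed.

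- f = 1%: 0.65/0.99 = 65.7%
- f = 3%: 0.65/0.97 = 67.0%
- f = 5%: 0.65/0.95 = 68.4%
- f = 10%: 0.65/0.90 = 72.2%

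These figures isolate one exclusion and do not predict the PP rate as a whole.

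**4. Near the goal.** With 188 subjects, 108 successes are needed (lower bound 50.04%). At 107/188 the lower bound is 49.5% and ITT misses. If two of the failures had no challenge and are removed, 107/186 has a lower bound of 50.1%.

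**5. Kaplan-Meier.** Take 122 composite successes in 188 (64.9%). Let k subjects fail only by acute failure or late repeat ablation, with no qualifying episode recorded. If they stay at risk without an event, and nothing else is censored, the curve ends at (122 + k)/188:

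| k | Share of 188 | Curve at 12 months | Excess over 64.9% |
|---|---|---|---|
| 2 | 1.1% | 124/188 = 66.0% | 1.1 points |
| 4 | 2.1% | 126/188 = 67.0% | 2.1 points |
| 9 | 4.8% | 131/188 = 69.7% | 4.8 points |
| 19 | 10.1% | 141/188 = 75.0% | 10.1 points |

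If they were instead censored at the start, the curve would end at 122/(188 − k), for example 122/179 = 68.2% at k = 9. The plan does not say which applies. Counting them as events returns the curve to 64.9%.

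**The case against.** Much can be said on the other side.

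- **PP keeps most failure types.** A reader might infer that acute failures and late re-ablations all drop out of PP, so that PP must overstate success. The table above does not support this: three of the five kinds are not on the list, and a fourth largely repeats the protocol's insertion requirement. Other listed violations (consent defects, missing thrombus examination, the excluded sheath, eligibility breaches, repeated catheter use) can remove successes. This stands.
- **PP sets normally drop subjects who miss a required step.** Protocol 5.4 requires the challenge. The documents also never separate untested subjects from those tested without block. But the acute-success definition needs confirmation with the challenge, so an untested subject fails on its wording, and the inclusion rule makes no exception for PP. Omission is plausible: Protocol 5.2 calls the challenge recommended while 5.4 and SAP 3.7 call it required, and these passages must be reconciled.
- **The Kaplan-Meier event is pre-specified and plainly named.** It carries no test against 50%, subjects are not removed from it, and SAP 6.5.1 and 6.5.2 report late repeat ablation and acute success separately. Many late re-ablations may follow an episode already counted. This stands: the curve is not wrong for its named event, replacing it is not warranted, and the excess shown is an upper limit. The mismatch with the primary definition remains, as does the missing censoring rule.
- **No decision depends on either analysis.** This also stands.

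**Conclusion.** The point holds in a limited form. Excluding subjects with no challenge conflicts with the rule that acute failures stay in the effectiveness cohorts, and taken alone it can only raise the PP rate: by 0.7 points at an assumed 1% of subjects and 3.4 points at 5%, from 65%. This rests on reading an untested subject as an acute failure, which is what the definitions say. The net difference between PP and ITT could go either way.

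The Kaplan-Meier curve can exceed the primary success rate by up to the share of subjects whose only failure is acute failure or late repeat ablation, about one point per 1% of subjects with other censoring set aside. The documents give no frequency for either group.

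It would be tempting to conclude that the superiority claim is inflated. It is not: ITT counts every failure type, and the missing-data sensitivity analysis drops only subjects not followed to the endpoint. The change is worth making because it is cheap and removes a one-directional distortion from each supporting analysis.

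**What to change.** **SAP 6.2.3.** Keep in PP, as failures, subjects who had the study catheter inserted and ablation performed and whose departure itself meets the acute-failure definition, that is, no isoproterenol confirmation. Leave the insertion requirement of Protocol 8.3 unchanged.

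**SAP 6.5.1.** Add a Kaplan-Meier analysis of the full primary-failure composite:

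- acute failure as an event at the start of the curve;
- otherwise the earlier of a repeat ablation after Day 90, at its date, and the first qualifying episode after Day 90;
- a stated censoring rule.

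Keep the pre-specified curve and label it as symptomatic episodes only.

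**Cost.** SAP wording and minor programming; the data are already collected under Protocol 5.8 and SAP 6.4. PP will keep a few subjects with a procedural departure, and the supporting figures become slightly less favourable.
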